# 4.3.5 Information on Haemophilia B Disease Related Surgeries and Joint Status

#### 4.3.5.1 Information on Haemophilia B Disease Related Surgeries

At the screening visit the following data is collected for disease related surgical history:

- Date of surgery
- Surgical event
- Preventive treatment during surgery: Recombinant or plasma product

The exact same information is also registred for general surgical history.

All data will be presented in listings.

#### 4.3.5.2 Joint Status

At screening the following data are registered:

- Joint status (Haemophilia joint health score version 2.1)
- Number and location of target joints
- Range of motion of joints

All the data will be presented in listings.

## 4.3.6 Lab Parameters for Evaluation of Patient Eligibility

The presentation of the data at the screening visit related to exclusion criteria 2 (FIX ihibitors as measured by the local laboratory), exclusion criteria 3 (neutralizing antibodies for AAV5), and excluson criteria 4 (serum chemistry) will be described in section 4.5. The data regarding exclusion criteria 5 and 6 are however only measured at the screening visit and these data will be presented in a separate listing. These specific data comprise the following laboratory parameters: HIV, CD4+, HIV viral load, HBsAg, HBeAg, HBVDNA, and HCV RNA.

Larix A/S - Strictly Confidential F501-0-1–5 SAP Template Page 16 of 34

Date: 27MAY2021

CT-AMT-060-01 EudraCT No.: 2013-005579-42 Statistical Analysis Plan Final no. 05 Page 17 of 34

# 4.3.7 Administration of IMP

All data registred regarding the administration of IMP at visit 2 will be presented in a listing.

# 4.4 Efficacy

# 4.4.1 Primary Efficacy Analysis

None of the efficacy endpoints are considered as primary endpoints. Refer to the next section.

## 4.4.2 Secondary Efficacy Analyses

#### 4.4.2.1 FIX Levels in Plasma

Blood samples for FIX activity will be collected at all visits. At Visit 2, blood sampling will take place prior to IMP administration.

Throughout the entire trial period (from Visit 1 and onwards) where a patient is on prophylactic FIX replacement therapy, it will be the aim to draw blood samples at time points where FIX activity is expected to be at the lowest levels. To the extent the visit windows allow, the investigator and/or study nurse will collaborate with the patient to schedule visits to take place on days where prophylactic FIX replacement therapy is planned to be administered. At these visits, blood sampling will then take place just prior to administration of prophylactic FIX replacement therapy.

The following FIX activity assays will be applied at the central laboratory:

- one-stage aPTT assay
- chromogenic/amidolytic assay

The data will be presented separately for each activity assay.

Absolute values will be listed and for each measurement the number of days since last FIX replacement therapy administration will be displayed.

The data will also be analysed descriptively by visit and cohort. These summaries will be generated both for a) all FIX measurements data b) FIX-replacement therapy free FIX measurements i.e. only measurement taken more than 10 days after the preceding FIX replacement therapy administration are included.

The procedure for calculating the above distance and defining latest FIX replacement therapy administration preceding the FIX activity measurement in question has been described in section 4.1. It is noted that if the date for a FIX replacement therapy administration is identical to the date of a FIX activity measurement and no time is indicated, then the FIX activity measurement in question is conservatively assumed to be contaminated i.e. as not FIX-replacement therapy free (the distance between the two time points will be calculated to 1 day).

For the one-stage aPTT assay data the patient individual profiles of FIX replacement free measurements in the period from last prophylactic dose (after tapering) until cut-off will also be presented. Regression lines will be presented and 95% confidence intervals will be displayed as part of legend for each patient.

## 4.4.2.2 Number, Severity and Type of Bleeding Episodes

In relation to the efficacy variables defined in this section and in section 4.4.2.3 a specific subset of the post-treatment period will be considered.

Larix A/S - Strictly Confidential F501-0-1–5 SAP Template Page 17 of 34 Date: 27MAY2021

Final no. 05

Page 18 of 34

CT-AMT-060-01 EudraCT No.: 2013-005579-42 Statistical Analysis Plan

For the interim analyses described in section 5 the end of this specific post treatment will simply be the specified cut-off date. For the final analysis, this will be the end of study date.

The start of this period is defined for each patient as the end of tapering, i.e. the date of the last prophylactic FIX replacement therapy administered. Before the data base freeze for an interim analysis in question (c.f. section 5) this start date will be decided on for each patient. The decisions made in connections with the first formal interim analysis (c.f. section 5) appear in Appendix 2.

As mentioned in section 4.3.4.3 all bleeding episodes occurring in the one year period prior to screening will be registered.

These data will be presented in a listing and also summarized with respect to annualized bleeding rate, and number of episodes. Separate summaries will be generated for all bleeds and for the different types of bleeds (spontaneous, traumatic, unknown, spontaneous+unknown). It is assumed that the bleeding episodes are observed during exactly one year i.e. the observed number bleeds will correspond exactly to the annualized bleeding rate for the 1 year prior to screening data for each patient.

From Visit 1 and throughout the entire trial participation period, patients will be asked to record information on bleeding episodes in an e-diary.

The patient e-diary will include questions regarding each bleeding episode with respect to

- Date and time of onset of bleed
- Date and time of stop of bleed
- Location of bleed (a number of categories have been defined in e-diary/eCRF)
- Circumstances of bleed (spontaneous, traumatic, minor surgery see definitions in protocol section 12.12)
- FIX replacement treatment of bleed (medication, dose, date and time of administration)
- Other therapy (pain relieving medication compression, ice)
- Investigator's evaluation of severity of bleed
- Evaluation of effect of treatment by patient (excellent, good, moderate, none), see definitions in protocol section 12.1.2)
- Evaluation of effect of treatment by investigator (excellent, good, moderate, none), in case bleeding episode requires hospitalisation or have a fatal outcome. It is noted that this assessment is registered on the (S)AE form.

It is noted that according to the protocol section 12.1.2 a bleeding episode is defined as a recurrent episode (re-bleed) if it is a worsening of symptoms in the same location after an initial period of improvement, either on treatment or within 72 hours after stopping treatment. If a bleed occurs in the same location later than 72 hours after stopping, the bleed is considered as a new bleed.

It is noted that a registration is made in the e-diary for each location for each bleeding episode i.e. if a bleeding episode occurs with more than one location this will be registered with multiple entries (one for each location) in the e-diary. Such multiple entries will be considered as separate bleeding episodes.

All the diary data and evaluations by the patient and investigator will be listed.

All bleeding episodes requiring FIX treatment from the post tapering period (end of prophylactic treatment until cut-off or end of trial) will be summarized in a similar same way as the bleeding episodes from the 1 year prior to screening period, with descriptive summaries of mean observation period and total observation period added. Total observation period (years) for each cohort is calculated as the sum of the observation periods of all patients in that cohort.

Larix A/S - Strictly Confidential F501-0-1–5 SAP Template Page 18 of 34

larix

Sponsor: uniQure

Date: 27MAY2021

CT-AMT-060-01 EudraCT No.: 2013-005579-42 Statistical Analysis Plan Final no. 05 Page 19 of 34

For this period the annualized bleeding rate is calculated as (number of bleeds \* 365.25)/ number of days in the period from last prophylactic dose until cut-off (or end of trial).

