14.2.2 Secondary Efficacy Endpoint Analysis

FIX Levels in Plasma

Data will be presented by subject, time point and dose level as summary tables and graphically.

Adjustment for time since most recent administration of FIX replacement therapy may be made, for example reporting by time less than 72 hours versus more than 72 hours after (reflecting prophylaxis free assessment). If applicable, the presentation will include summary statistics and confidence intervals for difference in FIX concentration between time-periods.

If applicable, the FIX level will be analysed using Non-Linear Mixed Models, possibly after transforming the data, and may include subject level random effect or subject level covariate to describe dependency between measurements. The analysis may include information on dose and timing of FIX replacement therapy. If relevant, the analysis may be extended to include modelling of values below lower level of quantification. The modelling may include subject level information on type of FIX replacement therapy, half-life, and if available previous knowledge of subject specific half-life for the FIX replacement therapy.

Number, Severity and Type of Bleeding Episodes

Bleeding episodes will be summarized by subject and overall, and will include number, duration and severity. Separate summaries may be made for bleeds depending on type and location, including target joints, and also summaries excluding recurrent bleeds.

Annualized bleeding rates overall and by severity will be presented. If relevant, summaries will be made using timing representing subject specific periods for pre-tapering, tapering period, and post tapering period until 26 weeks, and post 26 weeks.

Furthermore, the number of bleedings may be analysed using models for count data adjusting for time at risk using generalized linear model with Poisson or Negative Binomial distribution. Where description of timing and inter-event duration is of interest, models for time-to-event analysis may be used, such as Cox Proportional models or other parametric model, possibly including subject level frailty parameter. The analysis may include information on dose and timing of FIX replacement treatment, and measured FIX concentration.

Prophylactic and On-demand FIX Replacement Therapy

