## 4.3.4.3 Bleeding History from one year prior to screening

In a specific CRF module data regarding all bleeding episodes occuring in the one year period prior to the screening visit wil be registered. For each bleeding the following data will be recorded:

- Date of the bleed
- Type of bleeding (spontaneous, traumatic, unknown)
- If FIX replaceent therapy was used the name of the therapy and the total dose

These data will be listed and summarized as described in section 4.4.2.2 and 4.4.2.3. All data registered in the above mentioned CRF module will be included even if not complying strictly with the requirement of having occurred within one year (365 days) before the screening (Visit 1) date.

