Trial ID: CT-AMT-060-01 EudraCT No: 2013-00557942-42	Та	able Shells		Final Version 05 Page 22 of 66
Table 14.2.10 Summary of bleeding episode	s and annualized bleedin	g rates - All bleeds - Per	iod: One year prior to screening - FAS	6
	Cohort 1 (N=x) n (%)	Cohort 2 (N=x) n (%)	Total (N=x) n (%)	
Number of patients with bleed, n (%)	x (xx.x)	x (xx.x)	x (xx.x)	
Number of bleeds	x	x	x	
Bleeds per patient (min; max)	x; x	x; x	x; x	
Annualized bleeding rate				
n	х	х	x	
Mean (SD)	x.xx (x.xx)	x.xx (x.xx)	x.xx (x.xx)	
Median	x.xx	x.xx	X.XX	
Min ; Max	x.x; x.x	x.x; x.x	x.x; x.x	

N: Number of patients in Full Analysis Set (FAS). n: Number of patients with the parameter. SD: Standard Deviation. n\*: Number of bleeds. Severity: Assessment by investigator.

Cohort 1: AAV5-hFIX 5.0 x 10^12 gc/kg, Cohort 2: AAV5-hFIX 2.0 x 10^13 gc/kg

Only bleeds requiring on demand FIX infusion are included.

Sponsor: uniQure biopharma B.V	Date		larix	
Trial ID: CT-AMT-060-01 EudraCT No: 2013-00557942-42	Та	ble Shells		Final Version 05 Page 23 of 66
Table 14.2.11 Summary of bleeding episodes	and annualized bleeding	g rates - Spontaneous ble	eeds - Period: One year prior to screen	ing - FAS
_	Cohort 1 (N=x) n (%)	Cohort 2 (N=x) n (%)	Total (N=x) n (%)	
Number of patients with bleed, n (%)	x (xx.x)	x (xx.x)	x (xx.x)	
Number of bleeds	х	х	х	
Bleeds per patient (min; max)	x; x	x; x	x; x	
Annualized bleeding rate				
n	х	х	x	
Mean (SD)	x.xx (x.xx)	x.xx (x.xx)	x.xx (x.xx)	
Median	X.XX	x.xx	X.XX	
Min ; Max	x.x; x.x	x.x; x.x	x.x; x.x	

N: Number of patients in Full Analysis Set (FAS). n: Number of patients with the parameter. SD: Standard Deviation. n\*: Number of bleeds. Severity: Assessment by investigator.

Cohort 1: AAV5-hFIX 5.0 x 10^12 gc/kg, Cohort 2: AAV5-hFIX 2.0 x 10^13 gc/kg

Only bleeds requiring on demand FIX infusion are included.

Sponsor: uniQure biopharma B.V	Date 27MAY2021			larix
Trial ID: CT-AMT-060-01 EudraCT No: 2013-00557942-42	Та	ble Shells		Final Version 05 Page 24 of 66
Table 14.2.12 Summary of bleeding episodes	and annualized bleeding	g rates - Traumatic bleed	ds - Period: One year prior to screening	- FAS
	Cohort 1 (N=x) n (%)	Cohort 2 (N=x) n (%)	Total (N=x) n (%)	
Number of natients with bleed n (%)	x (xx x)	x (xx x)	x (xx x)	
Number of bleeds	X	X	x	
Bleeds per patient (min; max)	x; x	x; x	x; x	
Annualized bleeding rate				
n	х	х	x	
Mean (SD)	x.xx (x.xx)	x.xx (x.xx)	x.xx (x.xx)	
Median	x.xx	x.xx	X.XX	
Min ; Max	x.x; x.x	x.x; x.x	x.x; x.x	

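### SAP 4.4.2.2 counts all registered bleeds before screening but only FIX-treated bleeds after tapering; the prior-year table shells count treated bleeds only, and nothing says which rule prevails

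*SAP*

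**What the plan says.** **Prior year, text.** SAP 4.3.4.3 describes the source: "In a specific CRF module data regarding all bleeding episodes occuring in the one year period prior to the screening visit wil be registered". Treatment is a conditional item in that module ("If FIX replaceent therapy was used the name of the therapy and the total dose"), so untreated bleeds can be entered. SAP 4.4.2.2 refers back to this module and states: "These data will be presented in a listing and also summarized with respect to annualized bleeding rate, and number of episodes". Observation is taken as exactly one year, so that "the observed number bleeds will correspond exactly to the annualized bleeding rate for the 1 year prior to screening data for each patient". No treated-only filter appears.

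**After tapering, text.** The same section then summarises "All bleeding episodes requiring FIX treatment from the post tapering period". The ABR is bleeds times 365.25, divided by the days from the last prophylactic dose to cut-off or end of trial.

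**Shells.** Prior-year Tables 14.2.10 to 14.2.14 carry the footnote "Only bleeds requiring on demand FIX infusion are included". So do post-tapering Tables 14.2.15 to 14.2.17 and 14.2.19; 14.2.18 is specified by reference to 14.2.17. SAP Section 7 makes the shells part of the SAP without ranking them against the text.

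**Where the periods meet.** SAP 4.4.2.3 plans a patient-level listing that combines bleeding episodes and ABRs from both periods. The text states no filter for it. Its shell page is not in the public file, so nothing is inferred about its content.

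**Protocol.** Section 8.2.2 lists bleeding rate as a supportive efficacy endpoint, and Section 14.2.2 says "Annualized bleeding rates overall and by severity will be presented". Neither mentions a restriction to treated bleeds. SAP Section 6 lists one deviation only, the change from 72 hours to 10 days for FIX activity.

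**The concern.** The trial is uncontrolled, with five patients planned per cohort in the SAP, so its evidence on bleeding is largely each patient's rate after tapering set against his rate in the prior year. That comparison needs the same event counted on both sides.

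The text of 4.4.2.2 does not do this. Two programmers working from the same data, one following the text and one following the shells, could produce different prior-year ABRs and so different before/after contrasts. The text's rule can err in one direction only, because untreated bleeds are dropped only from the later period.

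Untreated bleeds are foreseeable. Protocol 12.1.2 has the e-diary record non-FIX measures such as compression and ice, and Protocol 11.4 leaves on-demand FIX to the investigator's discretion. Under either rule no all-bleed rate after tapering is tabulated.

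**Working it through.** The plan states no ABR value, sample-size calculation or power, so there is no figure to reproduce. The check applies the SAP's own two ABR rules to a patient whose true bleeding does not change.

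**Inputs**
- T: true bleeds per year, the same in both periods. T = 4 is used as an example; it is the on-demand entry threshold in Protocol 9.2, not an expected value.
- f: share of bleeds treated with FIX. The documents do not give it, so every value below is an assumption.
- Prior-year ABR: the count itself (SAP 4.4.2.2).
- Post-tapering ABR: count × 365.25 / days (SAP 4.4.2.2). An illustrative 4.75 years is used; the length cancels.

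**If the text is followed**

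Prior-year ABR = T. Post-tapering ABR = (f × T × 4.75) × 365.25 / (4.75 × 365.25) = f × T. Apparent fall = 1 - f.

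| Assumed f | Prior year | Post-tapering | Apparent fall |
|---|---|---|---|
| 1.0 | 4.0 | 4.0 | 0% |
| 0.9 | 4.0 | 3.6 | 10% |
| 0.75 | 4.0 | 3.0 | 25% |
| 0.5 | 4.0 | 2.0 | 50% |

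The percentages are the same at T = 2 and T = 8.

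**If the shells are followed**

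Prior-year ABR = f_pre × T. Post-tapering ABR = f_post × T. Apparent fall = 1 - f_post / f_pre.

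- Same share in both periods: 0%, whatever T and f.
- 0.90 before, 0.75 after: 3.6 to 3.0, and 1 - 0.75/0.90 = 16.7% apparent fall.
- 0.75 before, 0.90 after: 3.0 to 3.6, and 0.90/0.75 - 1 = 20% apparent rise.

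**If all bleeds are counted in both periods**

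The apparent change is 0% at any f, provided bleeds are captured equally well in each period.

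The two readings differ only in the prior-year figure, T against f_pre × T. They agree when every prior-year bleed was treated.

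**The case against.** The strongest reply is that the shells are like for like. Every prior-year ABR table and every post-tapering ABR table works to the same treated-only rule, and 4.4.2.2 says the later bleeds are to be summarised in much the same way as the earlier ones, which suggests that symmetry was intended. On that view the defect is a missing clause in one paragraph. This stands as far as it goes, but it does not say which rule governs, and the combined listing has no stated filter.

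Three stronger readings are tempting, and the documents do not support them.

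- *The shells mislabel treated bleeds as all bleeds.* In 4.4.2.2 that phrase stands in contrast to the causes (spontaneous, traumatic, unknown), so in the table titles it means all causes. The footnote discloses the restriction.
- *The SAP departs from an all-bleed endpoint fixed by the protocol.* The protocol says only bleeding rate, overall and by severity. Its history item in Section 12.3.6 itself counts bleeds that required treatment, although the SAP does not use that item as the source of the prior-year ABR. The restriction is unstated in the endpoint; it does not contradict it.
- *Counting treated bleeds biases the ABR downward because patients with higher FIX treat fewer bleeds.* That is a supposition. No passage gives a treated share or a trend, and under the shells the error can run either way. Protocol 11.4 says FIX should be given for any bleed, albeit at the investigator's discretion, so a large untreated share is not established.

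It is also fair to say that untreated bleeds are not hidden. All diary data and all prior-year bleeds are listed, and with about ten patients an all-bleed rate could be worked out by hand. The endpoint is supportive and no hypothesis is tested, so interpretation is at stake and not type I error.

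**Conclusion.** The inconsistency is real and should be corrected. As written, the text of 4.4.2.2 compares all registered bleeds before screening with FIX-treated bleeds after tapering, while the shells apply the treated-only rule to both periods, with no precedence between them.

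The size is conditional. Under the text, with a constant treated share, the spurious fall is 1 - f: 10% at an assumed 0.9, 25% at 0.75, none if every bleed is treated. Under the shells it is zero unless the treated share changes; assumed changes from 0.90 to 0.75 and from 0.75 to 0.90 give a 17% apparent fall and a 20% apparent rise. All of these shares are assumptions.

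A reader might infer that the reported ABR will be biased in favour of the product. The documents do not show that: it would require the text to be followed in programming and some prior-year bleeds to have gone untreated, and neither is established.

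**What to change.** 1. State one bleed definition for both periods in SAP 4.4.2.2, in the footnotes of Tables 14.2.10 to 14.2.19, and for the combined patient-level listing in 4.4.2.3. The definition should also cover bleeds at several locations: the e-diary counts each location as a separate episode, whereas the prior-year items listed in 4.3.4.3 include no location.
2. Tabulate two ABRs for each period, one for FIX-treated bleeds and one for all recorded bleeds, and say in the titles which is which.
3. Note in SAP Section 6 that the treated-only restriction is not stated in the protocol's bleeding-rate endpoint.
4. Beside the all-bleed comparison, state that prior-year bleeds come from a retrospective CRF module and later bleeds from a prospective e-diary. Minor untreated bleeds may be captured less completely in the former, so this comparison has an ascertainment difference of its own.

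The cost is wording changes and one extra set of tables. No new data are needed, since the plan already records treated and untreated bleeds in both periods. The sponsor may have to show a less favourable ABR alongside the treated-only one.

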20.1 Integrated Clinical Study Report

An interim analysis will be performed after all enrolled subjects have completed at least 52 weeks of follow-up after IMP administration (i.e. completed Visit 23). A database freeze will be performed. Collected efficacy and safety data will be analysed and reported in an interim CSR. The data will be considered locked at that point and will not be changed.

After all subjects have completed the 5-year visit (i.e. Visit 35), all collected safety and efficacy data will be locked, analysed, and reported in a full (5 year) CSR.

The full (5 year) CSR will also summarize contingency measures implemented to manage study conduct due to COVID-19 control measures, protocol deviations due to COVID-19, and the impact COVID-19 had on visit schedules, missed visits, and missing information.

The sponsor will notify the accredited IEC/IRBs and the regulatory authority of the end of the trial within a period of 90 days. The end of the trial is defined as the last subject's last visit.

In case the trial is ended prematurely, the sponsor will notify the IEC/IRB and the regulatory authority within 15 days, including the reasons for the premature termination. Within one year after the end of the trial, the Investigator/sponsor will submit the interim CSR and full (5 year) CSR with the results of the trial, including any publications/abstracts of the trial, to the accredited IEC/IRB and the regulatory authority.

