## 4.4.2.3 Prophylactic and On-demand FIX Replacement Therapy

As mentioned in section 4.3.4.3 administration on demand FIX replacement therapy in the 1 year period prior to screening has been registered. All these data will be listed. The on-demand FIX replacement therapy products used and the total dose used will be summarised for each cohort for this 1 year period prior to screening.

From Visit 1 and throughout the entire trial participation period, patients have been asked to document use of FIX replacement therapy in an e-diary. Two different modules in the e-diary will be used for registering prophylactic and on-demand FIX replacement therapy respectively.

The patient e-diary modules will include questions with respect to

- Date/time of administration
- Drug name
- Dose

All data will be presented in listings. The listings will be split two parts: a) the period from screening and until the end of tapering b) the period from end of tapering until end of trial/cut-off date in an interim analysis.

The use of prophylaxis and on-demand treatment in general will be summarized according to product and type (on-demand or prophylaxis). The summarises will be performed by cohort and overall. Furthermore, the total on-demand use for each patient (regardless of product) for the post tapering period will be summarized by cohort. The total dose for each patient will be annualized i.e. the dose will be adjusted for the length of the observation time (end of tapering until end of trial/cut-off date in an interim analysis) for the patient in question.

A listing will be generated combining on a patient level the information for the 1-year period prior to screening and for the post tapering-period including on-demand FIX-replacement therapy (annualized), bleeding episodes and annualized bleeding rates.

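### Read literally, the SAP annualises post-tapering bleeds and FIX use over days after a subject has left observation

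*SAP*

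**What the plan says.** SAP 4.4.2.2 treats the two ends of the post-tapering period differently. The start is individual: "The start of this period is defined for each patient as the end of tapering". The end is not. For interim analyses "the end of this specific post treatment will simply be the specified cut-off date", and the SAP continues: "For the final analysis, this will be the end of study date". The annualised bleeding rate (ABR) is bleeds times 365.25 divided by the "number of days in the period from last prophylactic dose until cut-off (or end of trial").

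SAP 4.4.2.3 annualises the FIX dose by "the length of the observation time (end of tapering until end of trial/cut-off date in an interim analysis) for the patient in question". The same window supplies the mean and total observation period rows of Tables 14.2.15 to 14.2.19.

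The documents use end of trial in two senses. Protocol 20.1 is trial-wide: "The end of the trial is defined as the last subject's last visit". Protocol Tables 5-4 and 5-5, however, label Visit 35 as End of Trial for the individual. Protocol 9.4 has a withdrawing subject called in for that visit unless he refuses further visits. Protocol 14.2 and SAP 4.1 both want subject-level summaries, the ABR among them, adjusted for observation time.

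**The concern.** Once a subject withdraws, dies or is lost, no further bleeds or infusions reach the e-diary. If the denominator keeps running to a common date, those days count as bleed-free and infusion-free although nobody observed them. The error goes one way: bleeding rate and FIX consumption, both named supportive efficacy endpoints, come out too low, and the printed observation time comes out too long. With about five subjects per cohort, one early exit can move a cohort mean visibly. It also conflicts with the plan's own principle, since time after exit is not observation time.

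**Working it through.** The documents give no ABR, exit date or dropout rate, so there is no stated figure to reproduce. The check applies the SAP formula to two windows.

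**Formula.** ABR = bleeds × 365.25 / D, where D is the days in the window. All recorded bleeds fall before exit, so the reported rate divided by the observed-time rate equals D(observed) / D(window), whatever the bleed count. The same ratio applies to annualised FIX dose.

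**Inputs.**
- Planned follow-up of 260 weeks (Protocol 10.1).
- Last prophylactic dose at week 10 (assumed; Protocol 11.4 places tapering in weeks 6 to 12).
- Exit week and bleed count (assumed).

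**1. Exit at week 104 with 4 treated bleeds, window run to week 260.**
- Observed: (104 − 10) × 7 = 658 days; 4 × 365.25 / 658 = 2.22 per year.
- Window: (260 − 10) × 7 = 1750 days; 4 × 365.25 / 1750 = 0.83 per year.
- Ratio: 658 / 1750 = 0.376, so 62% low.
- Other exits: week 52, 42/250 = 0.17; week 156, 146/250 = 0.58; week 208, 198/250 = 0.79.

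**2. Effect on a cohort of five**, each with a true rate of 2 per year, one leaving at week 104.
- Mean ABR: (4 × 2 + 2 × 0.376) / 5 = 1.75 instead of 2.00.
- Total observation: 5 × 1750 = 8750 days printed, against 4 × 1750 + 658 = 7658 observed. The excess is 1092 / 7658 = 14%.

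**3. Interim analyses.** SAP Appendix 1 gives cut-offs of 5 August 2016 and 12 May 2017. The DMC charter, whose final version is dated 30 December 2014, had to be approved before screening. Follow-up at the second cut-off is therefore at most 864 days (864 / 7 = 123 weeks), and nobody can have completed 260 weeks. SAP 5 also requires every enrolled patient to have attended Visit 23 (week 52) by then, so only later exits matter at that interim. For an exit at week 52:
- cut-off at that subject's week 60: (52 − 10) / (60 − 10) = 42/50 = 0.84 of the observed rate;
- cut-off at week 123: 42/113 = 0.37.

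**4. Final analysis, end of trial as in Protocol 20.1.** Early exits behave as in step 1. Completers are touched too. The minimum stagger in Protocol 10.1 from the first Cohort 1 subject to the fifth Cohort 2 subject is 2 + 84 + 4 = 90 days. The first completer's ratio is 1750 / (1750 + 90) = 0.951, about 5% low; a longer stagger makes it larger.

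**5. Final analysis, end of trial as the subject's own Visit 35.** Completers, and withdrawals who attend Visit 35, have no unobserved tail. For deaths, losses to follow-up and withdrawals without that visit, the SAP gives no end date.

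**The case against.** The best defence concerns the final analysis. The Protocol 20.1 definition stands beside the duty to notify authorities, not in the statistics section. Visit 35 is the End of Trial Visit for each subject, and withdrawing subjects are called in for it. SAP 4.4.2.3 speaks of time for the individual patient, SAP 4.4.2.2 sums patients' observation periods, and both documents ask for adjustment for observation time. A programmer could reasonably close each window at the subject's own last visit.

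That stands as a possible reading of the final analysis. It does not rescue the interim wording, which names one calendar date. Nor does it supply an end for anyone without a Visit 35. In SAP 4.4.2.3 the parenthesis itself defines the observation time as running to end of trial or cut-off.

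It is also fair that the analyses are descriptive, that diary bleeds, withdrawals and patient-level rates are listed so an affected subject could be spotted, and that both interim cut-offs precede SAP edition 05 (27 May 2021). These points limit the consequence but do not remove the gap.

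A reader might infer two stronger things:
- *That early Cohort 1 completers are certainly understated.* This holds only on the trial-wide reading, and it cannot arise at the interims.
- *That poor responders leave and so look better.* No document shows that anyone left early. Table 14.1.2 is a generic disposition shell. Protocol 6.7 and 11.4 let subjects with inadequate expression continue or resume FIX replacement within the trial.

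**Conclusion.** The point holds as a defect of the rule as written. At an interim, following the text puts unobserved time into the denominator of any subject who left before the cut-off. At the final analysis it does so on the Protocol 20.1 meaning of end of trial; on the Visit 35 meaning the problem shrinks to subjects with no defined end. Two programmers could derive different rates from the same data, and the literal derivation is the favourable one.

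The 62% understatement is an illustration. It rests on the assumed exit at week 104 and last prophylaxis at week 10, with the window run to week 260. The completer effect of about 5% is a minimum and belongs to the trial-wide reading alone. The actual effect is zero if nobody left early and Visit 35 closes each window. The text of SAP 4.7 and Appendix 2 was not available for this check. By title they cover visit assignment and the start of the post-tapering period, so they are unlikely to settle the end, but this could not be confirmed.

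**What to change.** In SAP 4.4.2.2 and 4.4.2.3, end each subject's window at the earliest of:
- the cut-off date (interim analyses);
- the date of withdrawal, death, or last e-diary or site contact;
- his own Visit 35.

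Use that one date for the ABR, the annualised FIX dose and the observation-period rows of Tables 14.2.15 to 14.2.19. Last contact should not be taken as the last bleed or infusion entry, because a bleed-free subject may have nothing to enter. The e-diary review, at least monthly after Visit 21 (Protocol 12.1.2), gives a usable contact date. If any subject left before an interim cut-off, check the interim rates against the same rule.

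The cost is two sentences and one derived date, which disposition and e-diary data should supply. The downside for the sponsor is that the rates may become slightly less favourable.
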